12.2.2 Registration and Eligibility

At the time of receipt of the signed consent form, the Sponsor medical monitor must be notified via email to initiate eligibility review. The study staff must include de-identified patient source documentation, the completed New Patient Registration Form (provided by the Sponsor) and a tentative therapy start date. Correspondence from the Sponsor for patient registration approval will be granted within 48 hours of receipt of adequate documentation.

A patient identifier will be assigned at the time of approval. Screening and eligibility MUST be entered into EDC within 7 business days of screening visit.

12.2.3 Patient Consent Form

Informed consent must be obtained before protocol-specified procedures or interventions are carried out. The investigator will explain the nature of the study and will inform the subject that participation is voluntary and that they can withdraw at any time. A copy of the signed consent form will be given to every participant and the original will be maintained with the subject's records.

The consent form must be approved by the IRB and be acceptable to the Sponsor. Consent forms must be written so as to be understood by the prospective subject. The Informed Consent should be translated and certified into the local language of the respondent, as deemed necessary. Informed consent will be documented by the use of a written consent form approved by the IRB and signed and dated by the subject and by the person who conducted the informed consent discussion. The signature confirms the consent is based on information that has been understood. Each signed informed consent form must be kept on file by the investigator for possible inspection by Regulatory Authorities and/or the Sponsor or its designee. The subject should receive a copy of the signed and dated written informed consent form and any other written information provided to the subjects, and should receive copies of any signed and dated consent form updates and any amendments to the written information provided to subjects.

12.2.4 Site Monitoring

To ensure compliance with current federal regulations and the ICH guidelines, data generated by this study must be available for inspection upon request by representatives of the FDA, national and local health authorities, the Sponsor and duly authorized representative of any entity providing support for this trial. Contractors of the Sponsor will conduct routine monitoring or audit activities for this study. The general scope of such visits would be to inspect study data (regulatory requirements), source documentation and CRF completion in accordance with current FDA Good Clinical Practices (GCP), the ICH guidelines and the respective local and national government regulations and guidelines.

12.2.5 Institutional Review Board Approval

This protocol, the informed consent document, relevant supporting information and all types of patient recruitment and advertisement information must be submitted to the local IRB for review and must be approved before the study is initiated. An amendment to remove a life-threatening situation can be implemented by the Investigator prior to obtaining IRB approval by the site. In such situations, the IRB must be notified immediately and the amendment forwarded to the IRB for their consideration.

The investigator is responsible for keeping their local IRB informed of the progress with study renewal at least once a year. The investigator must also keep the local IRB informed of any significant adverse events, per local institutional guidelines.

Records Retention: FDA regulations (21 CFR 312.62) require clinical investigators to retain all study- related documentation, including source document and CRFs, long enough to allow the sponsor to use the data to support marketing applications. If this study is conducted under an IND, all records must be maintained for:

- Two years after the FDA approved the marketing application, or
- Two years after the FDA disapproves the application for the indication being studied, or
- Two years after the FDA is notified by the sponsor of the discontinuation of trials and that an application will not be submitted.

For all studies, including studies with FDA-IND exemption, the Investigator/Institution/Sponsor will take measures to prevent accidental or premature destruction of study documents. For such studies conducted under IND exemption, records will be retained for a minimum of seven (7) years past official study termination.

13. STATISTICAL CONSIDERATIONS

13.1 Study Design

Arm A will accrue at least 16 evaluable patients. Arms B, D, and F will accrue 16-30 evaluable patients each. Arms C will accrue 6 evaluable patients who have sufficient resected tumor tissue for correlative studies. Arm E will accrue 12 evaluable patients who have sufficient resected tumor tissue for correlative studies. Patients in Arm C or E who after surgery are found to have insufficient resected tumor tissue for correlative studies will continue on treatment but will not count towards accrual of that arm. Data on these patients will be collected. In order to accrue 6 patients onto Arm C with sufficient tissue for correlatives following surgical resection, a total of 12 patients could be enrolled onto Arm C. In order to accrue 12 patients onto Arm E with sufficient tissue for correlatives following surgical resection, up to 18 patients could be enrolled onto Arm E.

The study duration is expected to be 7 years: 6 years for accrual, and 1 year for follow-up on the last participant enrolled.

Efficacy analyses will be performed separately for each arm. Patients enrolled in arms other than Arm D with a known H3 K27M mutation in their glioma may be included in the analyses of Arm D. Among recurrent glioblastoma patients, large meta-analyses of clinical trials evaluating a wide array of salvage therapeutics (excluding bevacizumab) have consistently reported PFS-6 rates of 9-11% ([Ballman 2007](#); [Lamborn 2008](#); [Wu 2010](#)). If the true PFS-6 rate on the current study for patients receiving ONC201 were 30% or higher, there would be interest in further investigation of this treatment regimen. Therefore, this study will be used to detect a difference of 20% using a one-

sided binomial test. Statistically, the hypothesis that will be tested is:

H0: $p \leq 0.1$ versus H1: $p > 0.3$

where p is the proportion of patients achieving PFS-6. Enrollment of 30 patients will yield 84% power to detect a 20% difference at an alpha level of 0.05 (one-sided exact test).

The primary efficacy endpoint is PFS-6, defined as the proportion of subjects in the analysis population who remain progression-free for at least six months following initiation of study therapy. Response for the primary analysis will be determined by the investigator assessment, and a confirmation assessment is required per RANO. If patients discontinue protocol therapy at or before 6 months without tumor imaging performed, the patient will be treated in the primary endpoint analysis as a treatment failure. Adjustments will not be made for multiple comparisons.

Secondary efficacy endpoints include: (1) ORR defined as the proportion of subjects in the analysis population who have complete response (CR) or partial response (PR) using RANO criteria; (2) duration of response, defined as time from first RANO response to disease progression in subjects who achieve a PR or better; (3) progression-free survival (PFS), defined as the time from initiation of study therapy to the first documented disease progression according to RANO or death due to any cause, whichever occurs first; and (4) overall survival (OS).

Additional supportive analyses of duration of response and PFS will be conducted using RANO criteria, in which a confirmation assessment of disease progression must be obtained at least 4 weeks after the initial disease assessment indicating progressive disease.

Safety will be assessed by quantifying the toxicities and grades experienced by subjects who have received ONC201, including serious adverse events (SAEs). Other safety endpoints include laboratory safety assessments, KPS status, and vital signs.

The predictive utility of intratumoral DRD5 expression will be evaluated in archival tumor specimens based on an inverse correlation with ONC201 efficacy in cancer cell lines. Among the 15 available archival tumor tissue specimens in Arm A, all had expression of DRD2 and 8/17 patients had low expression of DRD5. Patients with PFS > 5 months had no detectable expression of DRD5 unlike those with PFS < 5 months. In addition, 4/8 DRD2+DRD5- and 0/7 DRD2+DRD5+ patients were still alive with a median follow-up of 47.4 weeks. Based on these findings, DRD2+DRD5- patients are expected to have improved PFS and OS in response to ONC201 administration. For Arm B and Arm C, %DRD2 and %DRD5 positive cells (strong/total) will be quantified using image analysis algorithms for detection of DRD2 and DRD5 immunolabeling area and intensity (Visiopharm VIS software). Arms B and C will be combined for these analyses. Patients with pathologist-verified DRD5 staining area in the biopsy of >0.018% strong positive or >1% total positive will be classified as DRD5+. DRD5+ versus DRD5- patients will be compared for key clinical outcomes using a likelihood

ratio chi-square test (ORR) or log-rank test (PFS, OS). Significance will be declared if the two-sided p-value is <0.05 , with no adjustments for multiple comparisons. Because the assay for quantifying the %DRD5 strong positive cells or %DRD5 total positive cells is still being developed to be more precise, the data will also be normalized into Z-scores as a second and independent method of identifying patients as DRD5-positive or negative. Patients with negative Z-scores will be grouped into the DRD5- cohort and patients with positive Z-scores will be grouped into the DRD5+ cohort. The same comparisons for clinical outcome will be performed as above.

Pharmacodynamic effects will be evaluated by assessment of tissue biomarkers based on mechanism of action and preclinical tumor cell sensitivity studies. IHC ATF4, CHOP, and DR5 will be summarized using descriptive statistics.

Intratumoral ONC201 concentration in patients with recurrent GBM will be summarized using descriptive statistics separately for Arm C and E separately. A sample size of 6 achieves 80% power to detect a difference of -1.4 between the null hypothesis mean of 0.0 and the alternative hypothesis mean of 1.4 with an estimated standard deviation of 1.0 and with a significance level (alpha) of 0.05000 using a two-sided one-sample t-test. We are looking for an effect size of 2.9 since the target threshold for intratumoral drug concentrations is 2.9 uM representing the IC50 of ONC201 in cancer cell panels profiled for in-vitro efficacy.

Below you will find a table with calculations of minimal effect size corresponding to differing SDs for a sample size of 6 patients at 80% power and a two sided alpha of 0.5.

Power	N	Alpha	Beta	Mean0	Mean1	S	Effect Size
0.80000	6	0.05000	0.20000	0.0	1.4	1.0	1.435
0.80000	6	0.05000	0.20000	0.0	1.5	1.0	1.435
0.80000	6	0.05000	0.20000	0.0	1.6	1.1	1.435
0.80000	6	0.05000	0.20000	0.0	1.7	1.2	1.435
0.80000	6	0.05000	0.20000	0.0	1.8	1.3	1.435
0.80000	6	0.05000	0.20000	0.0	1.9	1.3	1.435
0.80000	6	0.05000	0.20000	0.0	2.0	1.4	1.435
0.80000	6	0.05000	0.20000	0.0	2.1	1.5	1.435
0.80000	6	0.05000	0.20000	0.0	2.2	1.5	1.435
0.80000	6	0.05000	0.20000	0.0	2.3	1.6	1.435
0.80000	6	0.05000	0.20000	0.0	2.4	1.7	1.435
0.80000	6	0.05000	0.20000	0.0	2.5	1.7	1.435
0.80000	6	0.05000	0.20000	0.0	2.6	1.8	1.435
0.80000	6	0.05000	0.20000	0.0	2.7	1.9	1.435
0.80000	6	0.05000	0.20000	0.0	2.8	2.0	1.435
0.80000	6	0.05000	0.20000	0.0	2.9	2.0	1.435

References

Zar, Jerrold H. 1984. Biostatistical Analysis (Second Edition). Prentice-Hall. Englewood Cliffs, New Jersey.

Report Definitions

Power is the probability of rejecting a false null hypothesis. It should be close to one.
N is the size of the sample drawn from the population. To conserve resources, it should be small.
Alpha is the probability of rejecting a true null hypothesis. It should be small.
Beta is the probability of accepting a false null hypothesis. It should be small.
Mean0 is the value of the population mean under the null hypothesis. It is arbitrary.
Mean1 is the value of the population mean under the alternative hypothesis. It is relative to Mean0.
Sigma is the standard deviation of the population. It measures the variability in the population.
Effect Size, $|\text{Mean0}-\text{Mean1}|/\text{Sigma}$, is the relative magnitude of the effect under the alternative.

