1.1 Study Design

This is a Phase II multi-center clinical trial with six arms and appropriate stopping rules for poor efficacy.

All subjects in Arm A will receive oral ONC201 every 3 weeks and all subjects in Arm B, C, D, E, and F will receive oral ONC201 every 1 week.

Arm A, B, D, and F will enroll 16-30 evaluable patients each. Arm C will enroll 6 patients who have sufficient resected tumor tissue for correlative studies. Arm E will enroll 12 patients who have sufficient resected tumor tissue for correlative studies. All subjects in Arm C and E will have surgical resection of their tumor 1 day after the second (or more) dose of ONC201.

All subjects will remain on study treatment until progressive disease, unacceptable toxicity, or withdrawal of consent.

All patients will undergo clinical evaluation after each cycle (3 weeks). Neuroimaging studies (contrast-enhanced brain MRI or CT for patients unable to undergo MRI) will be performed at baseline, at 8 weeks from treatment initiation, and then every 8 weeks thereafter.

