13.2 Interim Analyses

For Arm A, a futility interim analysis will be conducted after 16 patients are enrolled. Since PFS-6 requires at least six months post-study initiation follow-up for subjects without progressive disease, the binary endpoint PFS rate at two months (PFS-2) will be used to determine whether the accrual should be suspended after sixteen patients have accrued. If out of the first 16 patients enrolled, only 7 or less patients are observed to be progression free during the first 2 months after treatment initiation, further accrual in this arm will be discontinued. Assuming exponential distribution, the null and alternative for the PFS6 are translated into 0.44 vs. 0.67 rates for the PFS2. Under these rates the chances of observing 7 or less progression free patients out of the first 16 are 0.6 under the null and 0.046 under the alternative.

For Arm B, D, and F, separately, a futility interim analysis will be conducted after 16 patients who are evaluable for efficacy are enrolled. Since PFS-6 requires at least six months post-study initiation follow-up for subjects without progressive disease, the binary endpoint PFS rate at two months (PFS-2) will be one criteria used to determine whether the accrual should be suspended after sixteen patients have accrued. If out of the first 16 patients who are evaluable for efficacy are enrolled, there is no objective response and only 7 or less patients are observed to be progression free during the first 2 months after treatment initiation, further accrual in this arm will be discontinued. Assuming exponential distribution, the null and alternative for the PFS6 are translated into 0.44 vs. 0.67 rates for the PFS2. Under these rates the chances of observing 7 or less progression free patients out of the first 16 are 0.6 under the null and 0.046 under the alternative.

No interim analyses will be conducted for Arm C or E.

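### The stated 84% power holds for a fixed 30 patients with no interim; with the futility stop it is about 81–84%, and the final n, success count and H1 need stating correctly

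*Protocol*

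**What the plan says.** Protocol section 13.1 tests PFS-6 in each arm with a one-sided exact binomial test. The null is p ≤ 0.1 and the alternative is printed as p > 0.3. The sample-size statement is: "Enrollment of 30 patients will yield 84% power to detect a 20% difference at an alpha level of 0.05 (one-sided exact test". It does not mention the interim look and gives no number of successes needed to reject.

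Accrual is written as a range. Section 13.1 has "Arms B, D, and F will accrue 16-30 evaluable patients each" and, for Arm A, "Arm A will accrue at least 16 evaluable patients", with no upper limit. Section 1.1 gives Arm A the same range as the others: "Arm A, B, D, and F will enroll 16-30 evaluable patients each".

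Section 13.2 adds a futility look at 16 patients. For Arm A the condition is "If out of the first 16 patients enrolled, only 7 or less patients are observed to be progression free during the first 2 months", and the consequence is that "further accrual in this arm will be discontinued". For Arms B, D and F the stop also requires that no objective response has been seen. Section 13.2 reports the chance of 7 or fewer progression-free patients (0.6 under the null, 0.046 under the alternative) but no overall power or size. The SAP gives no sample size and lists no PFS-6 binomial test.

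**The concern.** The power figure describes a simpler design than the one planned. A futility stop can only lower the chance of a final rejection, so a figure that leaves it out is too high by some amount. The accrual range also leaves open how many patients an arm has at its final analysis, and the missing success count leaves open what result counts as positive. With an exact test these two belong together, because the cut-off moves in whole patients and power does not rise steadily with n.

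The printed alternative adds a separate problem. It leaves 0.1 to 0.3 in neither hypothesis and invites the reading that a rejection shows PFS-6 above 30%.

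At stake is whether a reader of a finished arm can tell what the rule was, how likely it was to detect a 30% rate, and what a positive result establishes.

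**Working it through.** **Inputs.** From section 13.1: p0 = 0.10, p1 = 0.30, one-sided α = 0.05, n = 30. From section 13.2: look at 16 patients, stop at 7 or fewer progression-free at two months, PFS-2 = 0.67 under the alternative. Assumed, because the documents do not give it: objective response rate (ORR) of 2–20%, independent of PFS-2.

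**1. The plan's own figure.** Take the smallest r with P(X ≥ r | n = 30, p = 0.10) ≤ 0.05.
- r = 6: size 0.0732, too large.
- r = 7: size 0.0258, power P(X ≥ 7 | p = 0.30) = 0.8405.

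The 84% reproduces, with no interim.

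**2. Adding the PFS-2-only stop (Arm A).** Among the first 16, the number progression-free at two months is X2 ~ Bin(16, 0.67). Given X2, the number reaching six months is Bin(X2, 0.30/0.67). The other 14 patients contribute Bin(14, 0.30). A stopped arm counts as not rejecting.
- P(X2 ≤ 7) = 0.047, matching the protocol's 0.046 to rounding.
- P(X2 ≥ 8 and total ≥ 7 of 30) = 0.812.
- Loss: 84.0 − 81.2 = 2.8 points.
- Size with the stop: 0.020 under the exponential model (null PFS-2 = 0.10^(1/3) = 0.464), or 0.018 with the protocol's 0.44. Both are below 0.0258.

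**3. Adding the rule for Arms B, D and F.** The stop also needs zero responses in 16 patients. Under independence this has probability (1 − ORR)^16, and it scales the loss in step 2:

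power = 0.8405 − (1 − ORR)^16 × (0.8405 − 0.8119)

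| Assumed ORR | (1 − ORR)^16 | Power |
|---|---|---|
| 2% | 0.724 | 82.0% |
| 20% | 0.028 | 84.0% |

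**4. If an arm passes the look but ends short of 30.** Here r is re-chosen at each n. The last column uses the PFS-2-only stop with PFS-2 = 0.30^(1/3) = 0.669.

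| n | r | Size, no stop | Power, no stop | Power with stop |
|---|---|---|---|---|
| 16 | 5 | 1.7% | 55.0% | 54.4% |
| 20 | 5 | 4.3% | 76.2% | 74.3% |
| 21 | 6 | 1.4% | 63.7% | 62.5% |
| 27 | 6 | 4.7% | 86.4% | 83.4% |
| 28 | 7 | 1.8% | 78.0% | 75.6% |
| 30 | 7 | 2.6% | 84.0% | 81.2% |

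Power falls from n = 20 to 21 and from 27 to 28. Over n = 16 to 30 the lowest value is at 16 and the highest at 27. Size at any n fixed in advance is at most 4.7%.

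**5. What a rejection shows.** The smallest success is 7/30 = 23%. Its one-sided 95% exact lower bound is 11.5%: above 0.10 and far below 0.30.

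**The case against.** The sponsor can fairly say that 84% is explicitly tied to 30 patients, is computed correctly, and is claimed for no other n. Sections 13.1 and 13.2 read together suggest 16 patients if stopped and 30 otherwise. On that reading power is a single figure for each rule, at most 3 points below the stated one, and H1 is a slip of notation in a paragraph that otherwise explains 30% as the rate of interest. Arm A is closed (section 8.3.3), so changing its target now alters nothing. All of this stands, and it limits the size of the point. It does not remove it: the protocol nowhere states the 16-or-30 rule or the cut-off, and the 84% leaves out the stop.

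Two stronger readings are tempting, and the documents do not support either.

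- A reader might infer that the design delivers anywhere from 55% to 86% power. Both ends are fixed-n values with no futility stop; with the PFS-2-only stop the range is about 54–83%. Either range also needs an arm to pass the look and then end short of 30, which the text neither plans nor excludes. An arm stopped for futility at 16 is already counted inside the 81%.
- A reader might infer that the open accrual range breaks the 5% level. Choosing the most favourable n from 16 to 30 with PFS-6 results in view gives 6.4%, but only if the stop is ignored. With the PFS-2-only stop the same exercise gives about 4.5–4.8%; under the rule for Arms B, D and F it lies between that and 6.4%, depending on response rate. The protocol plans no such choice, and section 13.2 itself notes that PFS-6 takes six months to observe.

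**Conclusion.** The point holds in limited form. The 84% is the power of a design without the interim. For an arm that continues to 30 after passing the look, it is about 81% under the PFS-2-only rule and about 82–84% under the rule for Arms B, D and F, an overstatement of 0–3 points. The final n for arms passing the look and the success count are not stated, and H1 is misprinted.

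The figures assume that PFS-6 is nested in PFS-2 with PFS-2 = 0.67 when PFS-6 is 0.30, that a stopped arm is not tested, and, for Arms B, D and F, the response rates above. Without the model linking PFS-2 to PFS-6, Arm A's power is at least 84.0 − 4.7 = 79.3% if PFS-2 is 0.67. The result is sensitive to that rate: under the PFS-2-only rule with n = 30, PFS-2 of 0.75 gives 83.6%, 0.60 gives 74.7% and 0.55 gives 66.4%. Testing a stopped arm at 16 with success at 5 or more would add about 0.6 points.

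**What to change.** In section 13.1:

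- State that an arm not stopped at 16 accrues to 30 evaluable patients, and bring the Arm A wording in sections 1.1 and 13.1 into agreement.
- Give the rule: success at 7 or more of 30, size at most 2.6%, and power at p = 0.30, including the stop, of about 81% (PFS-2-only rule) or 82–84% (Arms B, D and F, with the response-rate assumption stated).
- State that if an arm closes short of 30, the exact critical value and power for the n reached will be reported.
- Write the hypotheses as H0: p ≤ 0.1 versus H1: p > 0.1, powered at p = 0.3.

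This is a change of wording only. The cost is a stated power 0–3 points less favourable and the loss of discretion over an arm's final n. For Arm A, already closed, the change affects only how its result is described.

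### The DRD5 comparison pools Arm B with Arm C, which is resected on study, without stratifying by arm, and treated patients alone cannot show that DRD5 is predictive

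*Protocol*

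**What the plan says.** Protocol 13.1 sets the aim: "The predictive utility of intratumoral DRD5 expression will be evaluated in archival tumor specimens". For the new patients, "Arms B and C will be combined for these analyses". DRD5-positive and DRD5-negative patients are then compared with a likelihood "ratio chi-square test (ORR) or log-rank test (PFS, OS"). The decision rule is explicit: "Significance will be declared if the two-sided p-value is <0.05 , with no adjustments for multiple comparisons". No arm stratum, arm covariate or per-arm display is mentioned.

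The two arms are not the same. Protocol 1.1: "All subjects in Arm C and E will have surgical resection of their tumor 1 day after the second (or more) dose of ONC201". Protocol 3.1 (criterion 4) also requires Arm C patients to be candidates for salvage resection. Arm B has neither feature. On size, "Arms B, D, and F will accrue 16-30 evaluable patients each" and "Arms C will accrue 6 evaluable patients who have sufficient resected tumor tissue for correlative studies", with the allowance that "a total of 12 patients could be enrolled onto Arm C".

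Elsewhere the protocol keeps arms apart: 13.1 and 13.3 both call for efficacy to be analysed arm by arm. The SAP does not list the DRD5 analysis. Its section 3 says that protocol analyses it does not cover will either be left undone or be defined elsewhere.

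**The concern.** There are two separate problems.

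**Confounding by arm.** Fitness for resection, and the resection itself, may change PFS, OS or ORR whatever the DRD5 status. A pooled, unstratified test attributes any such arm difference to DRD5 in proportion to how unevenly DRD5 status falls across the arms. With 6 to 12 patients in Arm C, a lopsided split in the one sample actually obtained is possible. ORR has its own route to bias. Partial response is measured against baseline (Protocol 11.3.2), and baseline imaging precedes the first dose (Protocol 3.1, criterion 11; SAP section 2), so it precedes Arm C surgery. No post-operative re-baseline was found, and removal of tumour could therefore register as response.

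**The label.** Arms B and C receive the same weekly ONC201 (Protocol 5.1), with no untreated group. A DRD5 difference could reflect a better natural course or a better response to the drug, and these data cannot tell the two apart. A significant result reported under the protocol's stated aim would claim more than the design can show.

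**Working it through.** **1. Figures in the plan.** The documents give no power for the DRD5 comparison. The figure that sets Arm B's upper size does reproduce: with 30 patients, rejecting at 7 or more progression-free at six months gives exact one-sided alpha 0.0258 at 10% and power 0.8405 at 30% (stated 84%). The Arm A observation behind the hypothesis is 4 of 8 versus 0 of 7 alive. Fisher two-sided p = [C(8,4) + C(7,4)] / C(15,4) = (70 + 35) / 1365 = 0.077.

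**2. Assumptions (not in the documents).** Exponential PFS with Arm B at the null six-month rate of 10%: rate = −ln(0.10)/6 = 0.384 per month, median 1.8 months. Arm C versus Arm B hazard ratio (HR) from 1 down to 0.33. Where DRD5 is independent of arm, DRD5-negative prevalence is 8/15, as in Arm A.

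**3. Overall error, no DRD5 effect, DRD5 independent of arm.** 40,000 simulated trials per case, 12-month follow-up, B/C sizes 16/6, 30/6, 30/12 and 16/12, arm HR 1 to 0.33:
- pooled log-rank 5.5 to 6.5%
- arm-stratified log-rank 5.6 to 6.3%

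Rates are already 5.5 to 6.4% pooled when the arms do not differ, so the small excess over 5% is not caused by pooling.

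**4. Error given an uneven split.** Take 14/30 = 47% DRD5-negative in Arm B and 10/12 = 83% in Arm C. The DRD5-negative group then has 10 of 24 patients from Arm C, and the DRD5-positive group 2 of 18. At arm HR 0.5 the average starting hazards, relative to Arm B, are:
- DRD5-negative: (14 + 10 × 0.5)/24 = 0.79
- DRD5-positive: (16 + 2 × 0.5)/18 = 0.94

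This is an apparent HR of about 0.84 with no DRD5 effect. Simulated error rates with 24-month censoring (ranges are over repeated runs):

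| Arm C (DRD5-negative) | Arm HR | Pooled | Stratified |
|---|---|---|---|
| 12 (10) | 0.5 | about 10% | 5.4–5.7% |
| 12 (10) | 0.35 | about 15% | 5.8–6.5% |
| 6 (5) | 0.5 | 7.2–8.1% | 6.0–6.5% |

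Nearly all the pooled rejections with 12 in Arm C favour DRD5-negative.

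**5. How often such a split occurs.** With prevalence 8/15 in both arms and 30 in Arm B, exact binomial sums give a gap of at least 83% − 47% = 36.7 points in that direction with probability 1.7% for 12 in Arm C and 5.8% for six. Across the sizes in step 3, gaps of 40 points or more occur in about 1 to 4% of trials. Given such a gap, pooled error is 9 to 13% at HR 0.5 and 12 to 23% at HR 0.33; stratified it is about 5 to 7%.

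**6. If DRD5 status differed systematically by arm.** Assuming 45% versus 80% DRD5-negative, overall pooled error is 8 to 11% at HR 0.5 and 11 to 17% at HR 0.33; stratified 5.5 to 6.1%.

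**7. Power.** True DRD5 HR 0.4, 16/30 and 6/12 DRD5-negative:
- arm HR 0.5: 73–74% pooled, 78–79% stratified
- arm HR 0.35: 64–65% pooled, 78% stratified
- arms alike: 82% pooled, 79% stratified

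With six in Arm C and arm HR 0.5, stratifying gains about 3 points.

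**8. ORR.** Assuming 5% response in Arm B and 50 to 80% in Arm C, with DRD5 irrelevant, the pooled chi-square rejects in 6 to 9% of trials overall and in 22 to 59% given a gap of 40 points or more. With 12 in Arm C the conditional figures rest on about 400 runs. A stratified ORR test was not simulated.

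**The case against.** The best defence is that the arms are close. Both are first-recurrence Grade IV disease on the same schedule, with the same KPS floor and the same exclusions for prior bevacizumab and known IDH mutation. They are also the only arms where archival tissue is mandatory (Protocol 3.1, criterion 14), which is a natural reason to combine them. This supports pooling but does not argue against a stratum for arm, since resection remains a difference.

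Several stronger readings are tempting, and the documents do not support them:
- **Pooling inflates the test's error rate.** By chance imbalance alone it does not (step 3). The 10 to 15% applies only to an uncommon split, to assumed hazard ratios and to the Arm C ceiling of 12 rather than the planned six. A systematic link between DRD5 and arm would inflate it, but the documents neither show nor exclude one.
- **Pooling creates the predictive-versus-prognostic problem.** It does not; a stratified or Arm B-only test has the same limit.
- **Arm B is unresected.** Protocol 3.2 excludes only recent or unrecovered surgery. What can be said is that Arm B has no on-study resection.
- **DRD5 is the trial's main patient-selection hypothesis.** It is not named in sections 1.2 to 1.5, no eligibility criterion uses it and no decision rule follows. The listed objective in 1.3 is already one of correlation.

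It also stands that the analysis may never be run, since the SAP omits it. If it is run, Protocol 13.1 is the only specification in these documents.

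**Conclusion.** The point holds in a limited form. The pooled tests ignore a known difference between the arms, and if that difference affects outcome, the DRD5 contrast is biased whenever the realised split is uneven. For PFS the size ranges from negligible (about 6% overall, or about 7% versus 6% with six in Arm C under the assumed split) to material (10 to 15% with 12 in Arm C under that split). ORR could be worse because of the pre-surgery baseline. Every arm hazard ratio and response rate used here is an assumption.

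The power result does not need imbalance: stratifying gains roughly 6 to 13 points with 12 in Arm C if the arms differ at HR 0.5 to 0.35, and about 3 with six at 0.5.

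The conclusion about the label rests on no assumed figure. With every patient on ONC201, the analysis can establish association with outcome and nothing beyond it.

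**What to change.** In Protocol 13.1, or wherever the DRD5 analysis is specified given that the SAP does not list it:

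1. Stratify the log-rank tests for PFS and OS by arm (B, C).
2. Use an arm-stratified test for ORR, for example Cochran–Mantel–Haenszel, in exact form given the numbers.
3. Show DRD5 status and outcome for each arm beside the combined result.
4. Replace *predictive utility* with *association of DRD5 with outcome in ONC201-treated patients*, and state that predictive and prognostic effects cannot be separated.

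Stratifying the ORR test keeps a surgical effect from being attributed to DRD5. It does not settle what a response means in Arm C when the reference scan precedes surgery.

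The cost is a change of wording and one stratum term, and arm is already recorded. The price is about 3 points of power if the arms do not differ, and a weaker claim.
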